Intervention	All individuals residing in study localities will receive vector control preventative measures as per program. In the TPE arm, all individuals in the Target Area will receive dihydroartemisinin-piperaquine (DP) once daily for 3 days with the first dose taken no later than 5 weeks from the index case presentation (goal within one week). Individuals in RACD Target Areas will be tested by RDT and taken to the nearest health facility for treatment as per program operating procedures.
Evaluation methods	
The primary outcome measure of incidence will be obtained routine surveillance data. Secondary outcomes will be measured through Target area-level surveys:
 
1) Blood surveys. At the time of enrollment of a new Target area in RACD arm and at study conclusion in both arms (LAMP, QT-NASBA, serology, genotyping). DBS collected in incident cases as part of routine surveillance will also be utilized for genotyping.
 
2) Feasibility measurements: Coverage of RACD or TPE in the target population, serious adverse event (SAE) reports, costing of every 10th RACD and TPE event, pill count in TPE arm.
 
3) Acceptability assessment. Focus group discussions with TPE study participants and RACD/TPE surveillance team members.

Sample size	The sample size is based on the number of study localities that experienced at least one incident case of malaria in the previous season. Within 77 randomized localities, we expect that 63 localities will have an incident case of malaria and receive an intervention. For the primary objective, we hypothesize that TPE will be more effective than RACD. At the current sample size the study is powered to detect a difference in cumulative incidence if incidence in the TPE arm is reduced 50% compared to the RACD arm. Incidence will be measured at the locality level and among the at-risk population, or all individuals in an enumeration area (EA) where at least one case was identified (expected to be approximately 55928 among total study population of 211,189, or a harmonic mean of 656 per locality (41,328 effective population). Secondary outcomes of seroprevalence and prevalence will be measured on individuals residing in Target Areas (total N=5400) with a harmonic mean of 60 persons receiving intervention per locality (3780 effective population).
Primary outcome	Incidence of malaria cases

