14.3 Estimates of study power

Sample sizes and design effect estimates:

Sample size was driven by the number of localities within the area in the country considered to be at-risk for malaria transmission and the number of index cases we expect will be identified within those localities during the study period. The overall, Target Area, and adherence evaluation samples are described above in section 14.1. To estimate power to detect differences in cumulative incidence we used sample size of 55,928 for the overall sample. To estimate power to detect differences in seroprevalence, we used sample size of 5400 for the Target Area sample based on the assumptions as described above. As noted we used harmonic means for locality size (cluster size) in our estimates of power and design effect rather than arithmetic means to estimate more conservatively and to reduce the impact of the few localities with large population sizes.

We conducted sample size calculations to determine our ability to detect a difference in the effectiveness of TPE compared to RACD on incidence. We used the equations suggested by Hayes and Moulton (Cluster Randomized Trials, CRC Press, 2009) to calculate sample size required to detect a difference between arms.

Calculations are made for differences in proportion and assuming a coefficient of variation of 0.9 based on census and surveillance data from September 2012 to March 2015 to estimate the number of localities with cases, index cases and cluster size as described above. The power calculations are sensitive to sample size, but—in our study—the cluster population size is fixed. Sample sizes for primary and secondary outcomes can be found in Table 9.

Primary outcome – Cumulative Incidence:

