Our primary study outcome is cumulative incidence of passively detected malaria infections in the overall population of the randomized study area localities. If incidence in the RACD arm remains as it was during the 2012-2015 transmission seasons (during which RACD was the standard of care) then given the above assumptions, we would expect cumulative incidence in the RACD arm to be 0.4% or approximately 4 per 1000 persons. If this is the case, our study would have 80% power to detect a reduction in cumulative incidence to 0.2% or 2 per 1000 persons if at least 51 of the 77 study localities had at least one index case (Table 7). Should cumulative incidence in the RACD arm rise to 0.5%, the reduction to 0.25 or 2.5 per 1000 persons in the TPE arm would be detectable with at least 47 localities with at least one case. Should cumulative incidence in the RACD arm fall to 0.3%, reduction to 0.15% or 1.5 per 1000 persons in the TPE arm would be detectable with 57 localities with at least one case. Because of the clustered nature of the data and the variability in cluster size, we used the harmonic mean of the population size (656 per locality, or 41328 total population using the harmonic mean of locality population).

Secondary outcome of effectiveness – Seroprevalence:

In the end-line survey near the end of the study (expected mid 2017), non-index cases residing in Target Areas will undergo blood testing to measure seroprevalence. Index cases will also be included as long as they were not the first index case for a Target Area. The first index case will not be included as this person's malaria exposure was known to occur pre-intervention. The sample size for the seroprevalence measure is expected to be 5400. Based on preliminary data, we expect seroprevalence to be approximately 3% prior to any intervention.[6]

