End-line seroprevalence for RACD was calculated based on an estimate that only 20% of individuals with infection will be detected by RACD and treated, leading to a 20% effectiveness of RACD, or a drop from 3.0% pre-intervention to 2.4% end-line seroprevalence. We believe that TPE will be more effective than RACD in reducing seroprevalence near the end of the study (expected mid 2017). Because of the clustered nature of the data and the variability in cluster size, we used the harmonic mean number of observations expected per locality (60) to generate the effective sample size for analytic power (3780). Using these assumptions, our study would have 80% power to detect a decrease in seroprevalence to 1.18% in the TPE arm if 63 of the 77 localities had at least one case (Table 8).

Secondary outcome on feasibility – Coverage:

For the feasibility outcome measure on coverage, estimates were based on the goal TPE coverage of 80%. This goal is based on modeling data which suggests at least 80% coverage is needed for MDA to be successful, as well as experience from some settings that have successfully interrupted transmission in the setting of MDA [8, 18]. If estimates of incidence in the TPE arm are accurate, approximately 66 index cases will be identified and 1782 individuals will be treated in the TPE-assigned Target Areas. If the true coverage is 80% coverage, we would have a 95% confidence interval between 77% and 83% with this sample size [38].

Secondary outcome on feasibility – Adherence:

To measure adherence to DP, we will perform a pill count in individuals residing in the first Target Area for each TPE locality each transmission season. We will have 5% absolute precision to detect 80% adherence when the sample size reaches 532. If adherence is lower than expected, we will still have 10% absolute precision to detect 50% adherence when the sample size 208.

Table 7. Detectable Reductions in cumulative incidence given different assumptions about Incidence in the RACD

# Total localities with at least one index case	# localities per arm	Number assessed per locality (n)		Cumulative Incidence		Km (coeff of variation)	Z beta	Power
		RACD	TPE	RACD (π_0)	TPE(π_1)			
47.0	23.5	656	656	0.500%	0.250%	0.9	0.84	80%
50.6	25.3	656	656	0.400%	0.200%	0.9	0.84	80%
56.6	28.3	656	656	0.300%	0.150%	0.9	0.84	80%
61.4	30.7	656	656	0.250%	0.125%	0.9	0.84	80%
68.5	34.3	656	656	0.200%	0.100%	0.9	0.84	80%
80.5	40.2	656	656	0.150%	0.075%	0.9	0.84	80%

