Based on equation 4 from Hayes and Bennett International Journal of Epidemiology 1999;28:319-32

Assumes that population is only those in the EAs that have at least one case.

Sample size calculation based on harmonic mean of population size.

Table 8. Detectable reductions in seroprevalence given varying assumptions about prevalence in the RACD arm

# Total localities with at least one index case	# localities per arm	Number assessed per locality (n)		Outcome proportion		Km (coeff of variation)	Z beta	Power
		RACD	TPE	RACD (π_0)	TPE (π_1)			
46.6	23.3	60	60	3.00%	1.35%	0.9	0.84	80%
62.3	31.2	60	60	2.40%	1.18%	0.9	0.84	80%
49.3	24.7	60	60	2.00%	0.83%	0.9	0.84	80%
50.8	25.4	60	60	1.50%	0.57%	0.9	0.84	80%

Based on equation 4 from Hayes and Bennett International Journal of Epidemiology 1999; 28:319-326

Assumes we are including only persons in the target areas in the denominator but evaluating at locality level

Assumes 3 per 100 is the background seroprevalence

Table 9. Sample sizes for primary and secondary aims.

Outcome	Result*	Actual sample size (Effective sample size, based on harmonic mean in clusters)
Primary aim		
Incidence	0.4% (RACD) vs. 0.2% (TPE)	55,928 (41,328)
Secondary aims (effectiveness)		
Exposure (seroprevalence)	2.4% (RACD) vs. 1.18% (TPE)	5400 not including index cases (3720)
Infection prevalence	n/a	5600 includes index cases
Time to first post-intervention incident case	n/a	55,928 (41,328)

Outcome	Result*	Actual sample size (Effective sample size, based on harmonic mean in clusters)
Proportion of imported incident cases	n/a	55,928 (41,328)
Transmission potential	n/a	Genotyping estimated to be performed in 800 index cases** and 35 infections from follow-up cross sectional survey
Secondary aims (feasibility)		
Coverage in TPE Arm	80% (95% CI: 77%-83%)	1782
Adherence in TPE Arm	80%	532
Prevalence of SAEs related to treatment	n/a	5400 not including index cases (3720)
Acceptability	n/a	5400 not including index cases (3720)
Cost	n/a	10 Target Areas/arm

*for some secondary outcomes, power calculations were not performed however effective sample size is shown.

** 200 index cases will be from the study area but an estimated 600 DBS that are already collected as standard surveillance from other parts of the country will also be used to characterize the background genotypes/transmission potential in Swaziland, as it relates to the transmission potential in the study areas.

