For the primary analysis comparing incidence between the TPE and RACD arms, we will follow an intention-to-treat (ITT) approach. We hypothesize that cumulative incidence in the TPE localities will be lower than in the RACD assigned localities. For the initial ITT analyses, estimates of effect will be unadjusted for any variables other than intervention group. To check for possible contamination of effects by proximity to an index case treated with TPE, a second set of ITT analyses will be conducted adjusting for intervention group and distance of index case from an index case assigned to TPE. Outcomes are assessed at the individual level. Because of the clustered nature of the data, our modeling approach will also adjust for correlation of observations by locality for analyses using the overall sample and by locality and index case for analyses using the Target Area sample. Generalized estimating equations (GEE) will be used to perform the proposed primary analyses. GEE accounts for the correlation of persons within clusters and localities. GEE estimates are consistent even if the correlation structure is miss-specified, though GEE's statistical efficiency improves as the working correlation structure more closely approximates the actual correlation structure. Thus, several working correlation structures suitable for the study's design will be considered (e.g., unstructured, Autoregressive order 1, exchangeable). The QIC statistic will be used to select the final working correlation structure. Robust Huber-White "sandwich" standard errors will be used to obtain correct inferences even if

the chosen correlation structure remains slightly miss-specified. Alpha will be set at 0.05 for all planned comparisons.

Should the preliminary analyses reveal an imbalance in the baseline covariates between the TPE and RACD arms, a second set of models will be run for all primary analyses. Adjusted models will reweight the data (through inverse probability weighting, or targeted minimum loss based estimation) to recover effect estimates that reflect an equal distribution of baseline covariates.

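### Tables 7 and 8 report the localities needed per arm as the total for both arms; with the 63 localities expected, power is about 59% for incidence and 51% for seroprevalence, not 80%

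*Combined protocol and SAP*

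**What the plan says.** The Study summary expects 63 of the 77 randomised localities to have a case. It then states: "At the current sample size the study is powered to detect a difference in cumulative incidence if incidence in the TPE arm is reduced 50" percent relative to RACD.

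Section 14.3 gives the detail. For the primary outcome, with 0.4% in the RACD arm, it claims "80% power to detect a reduction in cumulative incidence to 0.2% or 2 per 1000 persons if at least 51 of the 77 study localities" have an index case. It says a halving from 0.5% is detectable with at least 47 localities, and that a halving from 0.3% "in the TPE arm would be detectable with 57 localities with at least one case". For seroprevalence, with 2.4% in the RACD arm, it says "our study would have 80% power to detect a decrease in seroprevalence to 1.18% in the TPE arm if 63 of the 77 localities" have a case.

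These figures come from Table 7 and from Table 8, titled "Detectable reductions in seroprevalence given varying assumptions about prevalence in the RACD arm". The first column of each table is headed as total localities with at least one index case. The second column, localities per arm, is half the first in every row. The calculations are described as "assuming a coefficient of variation of 0.9 based on census and surveillance data from September 2012 to March 2015". Section 14.4 gives the significance level: "Alpha will be set at 0.05 for all planned comparisons". It does not say whether tests are one- or two-sided.

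**The concern.** The standard formula for an unmatched cluster trial gives the number of clusters in each arm. Here its output seems to have been placed in the total column and then divided by two, so the per-arm counts would be half of what 80% power requires.

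This affects the power claim for the primary outcome and for seroprevalence, the only secondary effectiveness outcome with a power calculation. If the claims are wrong, a null result would be read as coming from a trial with 80% power when it had much less. Section 16.1 also has the safety monitoring committee review the protocol and analytical plan before the study starts, so that committee would be relying on the wrong figure.

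**Working it through.** **Inputs.** From Section 14.3 and Tables 7 and 8: k = 0.9; n = 656 people per locality for incidence and 60 for seroprevalence (harmonic means); z for power = 0.84; and the proportions π0 (RACD) and π1 (TPE) in each row. The other z is taken as 1.96 (two-sided 0.05). The plan does not state this, but it is the value that reproduces the tables. Expected localities: 63, or 31.5 per arm. Randomised: 77, or 38.5 per arm on average.

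**Formula.**

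V = π0(1−π0)/n + π1(1−π1)/n + k²(π0² + π1²)

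c = 1 + (1.96 + 0.84)² × V / (π0 − π1)²

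**Why c is a per-arm count.** V adds the variance of one locality's proportion in the RACD arm to the variance of one locality's proportion in the TPE arm. V/c is therefore the variance of the difference between arm means when each arm has c localities. This follows from the algebra and does not rest on the cited paper.

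**Primary row, 0.4% versus 0.2%.**

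- Sampling terms: 0.004 × 0.996/656 + 0.002 × 0.998/656 = 9.116 × 10⁻⁶
- Between-locality term: 0.81 × (0.000016 + 0.000004) = 1.62 × 10⁻⁵
- V = 2.532 × 10⁻⁵; V/(π0 − π1)² = 2.532 × 10⁻⁵ / 4 × 10⁻⁶ = 6.329
- c = 1 + 7.84 × 6.329 = 50.62

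Table 7 prints 50.6 as the total. It is the number per arm, so the total is 101.2.

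**Seroprevalence row, 2.4% versus 1.18%.**

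- Sampling terms: 0.024 × 0.976/60 + 0.0118 × 0.9882/60 = 5.847 × 10⁻⁴
- Between-locality term: 0.81 × (0.000576 + 0.00013924) = 5.793 × 10⁻⁴
- V/(π0 − π1)² = 1.1641 × 10⁻³ / 1.4884 × 10⁻⁴ = 7.821
- c = 1 + 7.84 × 7.821 = 62.32

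Table 8 prints 62.3 as the total. The true total is 124.6.

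**Power** for c localities per arm is Φ(√[(c − 1)(π0 − π1)²/V] − 1.96).

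- Incidence at the printed 25.3 per arm: √(24.3/6.329) − 1.96 = 0.00, giving 50%
- Incidence at 31.5 per arm: √(30.5/6.329) − 1.96 = 0.235, giving 59.3%
- Seroprevalence at 31.5 per arm: √(30.5/7.821) − 1.96 = 0.015, giving 50.6%

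**All ten rows.**

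| Table | RACD vs TPE | Printed total | Formula c (per arm) | True total | Power at 63 | Power at 77 |
|---|---|---|---|---|---|---|
| 7 | 0.5% vs 0.25% | 47.0 | 47.03 | 94.1 | 62.5% | 71.5% |
| 7 | 0.4% vs 0.2% | 50.6 | 50.62 | 101.2 | 59.3% | 68.2% |
| 7 | 0.3% vs 0.15% | 56.6 | 56.59 | 113.2 | 54.5% | 63.3% |
| 7 | 0.25% vs 0.125% | 61.4 | 61.38 | 122.8 | 51.2% | 59.7% |
| 7 | 0.2% vs 0.1% | 68.5 | 68.55 | 137.1 | 46.9% | 55.0% |
| 7 | 0.15% vs 0.075% | 80.5 | 80.50 | 161.0 | 41.1% | 48.5% |
| 8 | 3.0% vs 1.35% | 46.6 | 46.60 | 93.2 | 62.9% | 71.9% |
| 8 | 2.4% vs 1.18% | 62.3 | 62.32 | 124.6 | 50.6% | 59.1% |
| 8 | 2.0% vs 0.83% | 49.3 | 49.32 | 98.6 | 60.4% | 69.4% |
| 8 | 1.5% vs 0.57% | 50.8 | 50.79 | 101.6 | 59.2% | 68.1% |

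At the printed per-arm counts, power is 50% in every row after rounding.

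**Checks that do not depend on the algebra.** A simulation used gamma-distributed locality rates with CV 0.9, Poisson counts and a two-sided t-test on locality rates, with 20,000 runs. For incidence it gave 51–52% power with 25 and 26 localities, 61–62% with 31 and 32, and 83% with 51 and 51. For seroprevalence it gave 51–52% with 31 and 32, and 82% with 62 and 62.

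The printed totals are also too small at their limits. With no between-locality variation at all (k = 0), seroprevalence still needs 1 + 7.84 × 5.847/1.4884 = 31.8 per arm, or 63.6 in total, which is more than the 62.3 printed for k = 0.9. With an unlimited population per locality and k = 0.9, incidence still needs 32.75 per arm, or 65.5 in total, against 50.6 printed.

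**Effect detectable with 80% power at 63 localities.** Solving c = 31.5 for π1 gives 0.155% for incidence (a 61% reduction from 0.4%) and 0.77% for seroprevalence (a 68% reduction from 2.4%).

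**The case against.** The strongest objection is that 59% is only as firm as its inputs.

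- **Sidedness.** The plan gives alpha without it, and the hypothesis is directional. One-sided 0.05 raises incidence power at 63 localities to 71%.
- **Cluster size.** Section 14.3 says harmonic means were used "rather than arithmetic means to estimate more conservatively and to reduce the impact of the few localities with large population sizes". The arithmetic mean, 55,928/63 = 888, gives 64%, or 75% together with a one-sided test.
- **k.** This is the most influential input. Randomisation is stratified by risk rank and population, and the plan does not say whether 0.9 is an overall or a within-stratum value. If the relevant k were about 0.57, incidence power at 63 localities would reach 80%.
- **Consequence.** The number of localities is fixed by the at-risk area, so the error did not set enrolment. The last two rows of Table 7 already need more than 63 localities as printed, so 80% power was never presented as attainable there.

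These points limit how precisely 59% can be stated, and the corrected text should carry the conditions. They do not remove the error. Sidedness and cluster size together stop at 75% for incidence. A lower k would be a different assumption from the one the plan makes, and the initial primary analysis in Section 14.4 adjusts only for arm, which limits what stratification could recover. For seroprevalence at n = 60, no value of k makes the printed total right. A fixed number of localities explains why none can be added; it does not justify the 80% claim.

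**Conclusion.** The concern holds. The total column in Tables 7 and 8 is the per-arm requirement in all ten rows, and the per-arm column is half of what is needed. The true totals run from 93 to 161. On the plan's inputs, no row reaches 80% power even if all 77 localities have a case; the range at 77 is 49% to 72%.

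At the expected 63 localities, power is 59% for 0.4% versus 0.2% incidence and 51% for 2.4% versus 1.18% seroprevalence. A true halving of incidence would be missed about four times in ten.

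These figures assume k = 0.9, two-sided 0.05, harmonic-mean locality sizes and an even split of 63. A noncentral-t calculation gives the same 59% and 51%. Section 14.1 elsewhere expects only 22 TPE localities with an index case; if that applied, power would be lower still.

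**What to change.** 1. In Tables 7 and 8, head the first column as localities per arm and replace the totals. Table 7: 94.1, 101.2, 113.2, 122.8, 137.1, 161.0. Table 8: 93.2, 124.6, 98.6, 101.6.
2. Correct the statements in Section 14.3 for 47, 51, 57 and 63 localities, and the sample size entry in the Study summary. Possible wording: *Assuming k = 0.9, a two-sided 5% test, harmonic-mean locality sizes and 63 localities split evenly, the study has 59% power for a reduction in cumulative incidence from 0.4% to 0.2%; 80% power requires a reduction to about 0.155%. For seroprevalence, power is 51% for 2.4% versus 1.18%, and 80% power requires about 0.77%.*
3. Table 9 prints effect pairs without a power figure. Add a note giving the power at which each pair is detectable.
4. State whether the test is one- or two-sided, which case definition and period k = 0.9 was computed on, and whether it is an overall or a within-stratum value.
5. Show power on both sides of k = 0.9. With illustrative values (assumptions, not taken from the plan), incidence power at 63 localities is about 76% at k = 0.64, 66% at 0.79, 59% at 0.9 and 48% at 1.11.

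The cost is wording and table corrections only. Design, enrolment and conduct do not change; the stated power becomes less favourable.

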The sample size for the Target Area assessments is estimated from incidence in the previous transmission season, and the expected drop in incidence among those in the TPE arm; resulting in an estimated 200 index cases total with 30 individuals screened or treated in the Target Areas around each case. With 200 index cases, we expect about 6000 encounters where individuals will receive a study intervention (either TPE or RACD). Based on preliminary RACD data, we anticipate 10% of these encounters will occur in individuals who previously received an intervention during the study period (repeated or overlapping Target Areas). For the follow-up end-line seroprevalence survey, these individuals will only be sampled once. Thus the effective sample size for the seroprevalence outcome measured in the Target Area population is expected to be 5400. Of note, the first index case for each Target Area will not be included since this person's malaria exposure occurred pre-intervention.

For the follow-up end-line infection prevalence survey, index cases will also be included as they will also be at risk for subsequent infection. Thus the effective sample size for the infection prevalence outcome measured in the Target Area population will be 5400 individuals screened plus 200 index cases, or 5600 individuals.

Adherence evaluation:

Adherence will be measured on a subsample that includes only the individuals in the Target Areas surrounding the first index case in each locality. We expect that 22 localities in the TPE arm will have at least one index case, and at least 30 individuals will be assessed for DP treatment per Target Area, for a total sample of 660 individuals.

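### Table 8's harmonic mean of 60 people per locality does not share a basis with the 5,400 people behind the seroprevalence power; on that basis it is roughly 42, which costs about 7 points of power

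*Combined protocol and SAP*

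**What the plan says.** Two sizes are given for the seroprevalence sample.

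- **Total.** Section 14.1 describes the index-case estimate as "resulting in an estimated 200 index cases total with 30 individuals screened or treated in the Target Areas around each case". That is 6,000 encounters. A 10% deduction for people met more than once leaves 5,400, and section 14.3 says the seroprevalence power uses this figure.
- **Per locality.** Section 14.3 states that "we used the harmonic mean number of observations expected per locality (60) to generate the effective sample size for analytic power (3780"). The Study summary repeats it: "with a harmonic mean of 60 persons receiving intervention per locality (3780 effective population"). Table 8 enters 60 in both the RACD and the TPE column. Table 9 prints the effective size as 3,720.

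The power claim is that "our study would have 80% power to detect a decrease in seroprevalence to 1.18% in the TPE arm if 63 of the 77 localities" have a case. The RACD value comes from "a drop from 3.0% pre-intervention to 2.4% end-line seroprevalence", and the calculation is made "assuming a coefficient of variation of 0.9".

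For the TPE arm alone, the coverage paragraph of section 14.3 expects that "approximately 66 index cases will be identified and 1782 individuals will be treated in the TPE-assigned Target Areas". Table 8 has 31.2 localities per arm in the relevant row, while the adherence paragraph of section 14.1 expects 22 TPE localities with an index case.

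**The concern.** The total and the per-locality size should describe the same people. If 5,400 people come from 200 index cases, the harmonic mean per locality has to come from how those 200 cases fall across localities. The plan shows no such step, and 60 looks too large for a distribution as skewed as Table 2, where 23 of the 63 localities with cases had only one.

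Seroprevalence is the only secondary effectiveness outcome with a stated power. At n = 60 about half of the variance in the power formula is sampling error within localities, so an overstated n overstates the power and understates the difference that can be detected.

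**Working it through.** **1. Reproducing Table 8.** The inputs are p0 = 0.024, p1 = 0.0118, k = 0.9, n = 60 and z = 1.96 and 0.84. Section 14.4 says "Alpha will be set at 0.05 for all planned comparisons" without giving sidedness; two-sided is assumed. The unmatched cluster formula cited under the table is

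c = 1 + (1.96 + 0.84)² × V / (p0 − p1)², with V = [p0(1 − p0) + p1(1 − p1)]/n + k²(p0² + p1²).

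- Sampling term: (0.023424 + 0.011661)/60 = 0.000585
- Between-locality term: 0.81 × (0.000576 + 0.000139) = 0.000579
- V = 0.001164 and (p0 − p1)² = 0.00014884
- c = 1 + 7.84 × 0.001164/0.00014884 = 62.3

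This matches the printed figure. However, the formula returns localities **per arm**, and Table 8 prints 62.3 as the total. That is a separate error. It matters here because it fixes the baseline: 63 localities in all means about 31.5 per arm.

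**2. What the 200 index cases give.** Table 2 has 333 cases in 63 localities (maximum 41). The arithmetic mean is 5.29 and the harmonic mean is 63/32.417 = 1.943. People per index case are 5,400/200 = 27 after the repeat deduction, or 30 before it. The plan does not say how the 200 cases spread, so several rules were tried.

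| Spread of 200 index cases over 63 localities | n at 27 per case | n at 30 per case |
|---|---|---|
| Pure proportion to Table 2 (1.943 × 200/333) | 31.5 | 35.0 |
| Proportion, rounded, at least one case each (sums to 205) | 42.2 | 46.8 |
| One each, other 137 drawn at random in proportion to (cases − 1) | 42.1 | 46.7 |
| One each, other 137 shared in proportion to (cases − 1) | 45.8 | 50.8 |
| One each, other 137 drawn at random in proportion to cases | 48.1 | 53.4 |

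The first row leaves many localities with less than one case, so it is a lower limit. The unreduced 333 cases at 30 people each give 1.943 × 30 = 58.3, the simple product closest to 60.

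**3. The TPE arm.** 66 × 30 × 0.9 = 1,782. Over 31.5 localities this is an arithmetic mean of 56.6. A harmonic mean cannot exceed the arithmetic mean, so on these figures 60 is too large for TPE.

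**4. Effect on power.** Power = Φ{√[(c − 1)(p0 − p1)²/V] − 1.96}. At c = 31.5 per arm:

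- n = 60: √(30.5 × 0.00014884/0.001164) − 1.96 = 0.015, power 50.6%
- n = 42: V = 0.000585 × 60/42 + 0.000579 = 0.001415; 1.791 − 1.96 = −0.169, power 43.3%

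| n per locality | Power, 31.5 localities per arm | Localities per arm for 80% |
|---|---|---|
| 31.5 | 37.4% | 90.2 |
| 42 | 43.3% | 75.5 |
| 50.8 | 47.2% | 67.9 |
| 60 | 50.6% | 62.3 |

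With 31.5 localities per arm, 80% power against 2.4% requires a TPE seroprevalence of 0.77% at n = 60, or 0.64% at n = 42.

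**5. Effective size.** 63 × 60 = 3,780 and 62 × 60 = 3,720, so the two printed effective sizes appear to differ only in the locality count.

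**The case against.** The strongest reply is that 30 is a minimum per Target Area, not an expectation. Section 4.4 puts about 53 residents within 200 m of an index case, RACD areas extend to 500 m, and the end-line survey invites all residents, treated or not. At 53 people per case, before any repeat deduction, the rounded spread gives a harmonic mean of about 83. This stands as a reason not to call 60 too high in absolute terms. It does not rescue the plan as written, because 5,400 and 1,782 would then be wrong.

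A reader might infer that 60 is impossible in the TPE arm. The documents do not support that. The contradiction needs 27 people per case and about 31 localities together. With 22 TPE localities the mean is 1,782/22 = 81, and with 30 people per case it is 66 × 30/31.5 = 62.9. If 1,782 counts only people treated at 80% coverage, residents number about 2,228, or 70.7 per locality. The text also gives 60 as a pooled figure, and the pooled arithmetic mean is 5,400/63 = 85.7. Taking 22 localities does not restore the power, though: applied to both arms with n = 81, as a simplification, it gives 42.0%.

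The spread is an assumption too. Giving each locality 1 + 137 × cases/333 index cases, fractions included, yields 57.7 at 27 per case and 64.1 at 30. Localities cannot have fractions of a case, and drawing whole cases under the same rule gives 48.1 and 53.4. Still, no single replacement value is a plan figure.

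Finally, the outcome is secondary, the number of localities is fixed by geography, and nothing in conduct changes. That limits the weight of the point but does not remove it.

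**Conclusion.** The point holds as an unsupported input behind a stated power. The 60 and the 5,400 do not rest on the same count of people. On the 5,400 basis, with the Table 2 skew, n per locality is roughly 42, with a range of about 32 to 53. At the 31.5 localities per arm that the trial would have, moving from 60 to 42 lowers power by 50.6 − 43.3 = 7.3 points; at n = 51 the loss is about 3 points. This assumes two-sided alpha, k = 0.9, 2.4% against 1.18%, and 63 localities with a case split evenly.

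A reader might infer that the stated 80% falls to about 72%. That drop (79.9% to 71.9%) appears only if 62.3 localities are available in each arm, 124.6 in total, and the trial has 77. The plan's own formula at n = 60 already gives about 50%, so the per-arm mislabelling, at about 30 points, is the larger error. The harmonic-mean input comes on top of it and would remain after that column is corrected.

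That 60 was taken from the full 333 historical cases is plausible but not shown.

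**What to change.** In section 14.3, Tables 8 and 9 and the Study summary, derive n per locality by arm on one stated basis. There are two consistent choices:

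- keep 200 index cases with 27 distinct people each, and replace 60 and 3,780/3,720 with the harmonic means that follow; or
- base n on all residents to be surveyed at end-line, and change 5,400 and 1,782 to match.

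Either way, state the assumed spread of index cases over localities and use one count of TPE localities with a case (22 or about 31). Then restate the localities needed, the power and the detectable seroprevalence together with the corrected per-arm column of Table 8.

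The cost is recalculation and wording, with no change to enrolment or conduct. The downside is a less favourable stated power for a secondary outcome if the first basis is kept.
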